Three regional fiscal units in Helsinki (Europe), London (Canada), and Pittsburgh (USA) will be responsible for operations in these respective regions, and for acquisition and transfer of data to the DMU in Tampa, Florida. However, for governance purposes North America and Europe constitute two governance regions. Communication among participants in each region will be largely by electronic means, but group meetings will be essential during the initiation of the study, and throughout the recruitment and treatment phase. Special provision will be required for communication among, and support of, the trial coordinators modeled after the DCCT and its epidemiological follow-up (EDIC).

Committees

The two Regional Executive Committees will maintain effective electronic communication among the regions, with personal meetings of representatives as needed, through the TRIGR International Executive Committee (IEC). This coordinating committee will be under the Chairmanship of the lead principal investigator or his delegate, with the co-chairmanship of the national coordinators in Canada and United States or their delegates, and with representation of the several constituencies in the study groups.

The Data Safety and Monitoring Board supervises the safety issues in the study, and performs the interim analyses, described above. It also supervises compliance issues, like the interpretation of CM antibody assays.

Communication

During randomization and recruitment, rapid communication between each center, the genetics laboratories and the central randomization center is essential. This will be achieved by the development of an internet website with Email and fax backup. Once established, this communication format will be used throughout the study.

Participating centers

The study group members represent a versatile and high-standard expertise in the fields of pediatrics, pediatric diabetology, infant nutrition, pediatric gastroenterology, neonatology, obstetrics, nutrition science, genetics, immunology and epidemiology. Many members are internationally recognized experts in their fields related to research on type 1 diabetes, particularly on the etiology, pathogenesis and prevention of the disease, and they have published extensively on the prediction, prevention and etiology of type 1 diabetes. In addition, most centers in all regions have had substantial clinical trial experience in diabetes.

R. ANCILLARY STUDIES OUTSIDE THE CORE PROTOCOL

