Nineteen out of 325 offspring (5.9%) with increased genetic risk according to the criteria used in the Pilot-2 trial tested positive for at least one autoantibody by the age of 2.4 years in the German BABYDIAB study (107). Seventeen of these 19 subjects (89%) developed multiple autoantibodies during prospective observation. Assuming a constant increase in autoantibody frequency from age 2 to

age 6 years, the expected cumulative incidence of at least one antibody would be 14.8% and that of at least two antibodies 13.0% by the age of 6, which is well within the 95% CI of the observed frequency of 20.7% of multiple autoantibodies in the young DiMe siblings.

The cumulative incidence of at least one autoantibody by the age of 4 years was 10.6% in siblings and offspring of affected subjects in the DAISY study from Denver (108). The frequency reached 37.9% in those carrying the DR3/4, DQB1*0302 combination. Published data are not available allowing an estimation of the frequency of at least one or at least two autoantibodies in subjects with increased genetic risk as defined in the Pilot-2 trial. Nevertheless a constant increase in the frequency of at least one autoantibody from age 4 to age 6 years, would result in an autoantibody prevalence of 15.9% by the age of 6 years in siblings and offspring irrespective of HLA-defined genetic risk. The DiMe study was used for the power calculation as it includes the largest long term follow-up of young relatives.

The estimation that 2032 infants should be randomized for the trial (Table 1) is based on the following assumptions:

1. a confidence level of 95%;
2. a statistical power of 80%;
3. a reduction of 40% in the hazard rate of type 1 diabetes in the intervention group;
4. a drop-out rate of 20%; and
5. a frequency of 10% of exclusive breast feeding (BF) up to the age of 6 months

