The Nutrition Epidemiology Unit ([name], National Institute for Health and Welfare, Helsinki, Finland) of the International Coordinating Center is responsible for the education and supervision concerning the assessment and maintenance of the dietary compliance and the dietary advice given by the centers involved. A continuous quality control system is implemented in each center for the data collection and content, especially to ensure that the delivery of dietary advice and the measurement of dietary compliance function properly. A specially trained Study Monitor supervises the implementation of these measures. A Nutrition Fellow at the Nutrition Epidemiology Unit oversees the dietary intervention closely supervised by [name], by means of data collected, reports from the monitors, and continuous contacts with the Study Centers.

H. STUDY ASSESSMENTS

Baseline

After the delivery medical and perinatal history of the infant and mother (including birth weight and gestational age) and the results of the newborn physical examination are recorded on the case report forms.

Follow-up Period during and after Intervention

The subjects visit the research center or have a home visit at the age of 3, 6, 9, 12, 18 and 24 months, and at 3, 4, 5, 6, 7, 8, 9 and 10 years of age, or when clinical diabetes develops.

Protocol change in 2011: The follow-up of the subjects will be continued until the youngest participant reaches the age of 10 years. The oldest participants will then be 14-year old. During the prolonged follow-up period the follow-visits will take place annually at the ages of 11, 12, 13 and 14 years. The presence or absence of diabetes is determined according to the criteria outlined below (see Outcome Assessment, below). Clinical findings at each visit (e.g. weight, height) are recorded on the case report forms.

Protocol Change in 2015: Puberty will be assessed based on hormonal analyses. Serum estradiol will be analyzed in girls and serum testosterone in boys starting from the age of 8 years. In addition girls will be asked about their age at menarche and the use of medication containing estrogens and/or androgens starting from the age of 10 years.

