Blood for serology (diabetes-associated autoantibodies and CM antibodies) is drawn after the application of an analgesic ointment on the venipuncture site at the above mentioned visits and serum samples are stored centrally. In addition, the 3 and 6 month serum samples are available for use in the assessment of dietary compliance. All serum samples are aliquoted, and the samples are stored at -70 C° in the TRIGR Core Laboratory in Helsinki. Local measurement of plasma glucose and glycated hemoglobin takes place at 12, 18, 24 months, and 3, 4, 5, 6, 7, 8, 9 and 10 years. During the prolonged follow-up period these measurements will be performed at the age of 11, 12, 13 and 14 years. The specimens for plasma glucose are preferentially taken 1-2 hours postprandially. If the glycated hemoglobin is higher than the reference range, an OGTT may be required to confirm the diagnosis as below. An OGTT will be performed at the age of 6 and 10 years in all study subjects. In addition, an

OGTT will be performed in all study subjects at the last follow-up visit in 2016-2017. A heparin blood sample (3-5 ml blood depending on age) is obtained at each sampling time for the isolation of mononuclear cells. These cells are sent fresh to central labs (Professors [name], Helsinki, Finland and [name], Toronto, ON, Canada) and used for mechanistic studies. An EDTA blood sample, 4 ml, for DNA extraction will be collected from all study participants. Samples will be obtained in association of collection of blood samples for autoantibody analyses once at the age of 5 years or later. In the case of children who already have developed type 1 diabetes or have dropped-out from the follow-up a separate sample will be collected if possible.

Protocol Change in 2015: After TRIGR, any remaining samples will be placed into the National Institutes of Health (NIH) repository for future studies related to type 1 diabetes and its complications. They will be stored there indefinitely without names or any other identifying information on them. Once the samples are in the repository, subjects will not be able to have them removed. Researchers must first get permission from the NIH to use samples from the repository.

A summary and timetable of the various events are given in Table 3.

Table 3. Study schedule

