and the outcome variables (e.g., the status of the diabetes-associated antibodies). At every time point the single antibody variable will be dichotomized as negative or positive, and a summary variable will be produced (negative if less than two variables are antibody positive and positive if two or more variables are antibody positive). The exposure to formula vs. placebo will be included in the model as an indicator variable. Age at initiation, duration of breast feeding and/or formula use and cumulative formula dose will be included in the model as potential effect modifying and confounding factors. The presence of interactions will be tested and the possible effect of the components considered will be estimated.

Two different statistical methods will be used to analyze the hypothesis that weaning to a casein hydrolysate decreases the occurrence of diabetes-associated antibodies. First, generalized linear models will be fitted to the data (20). Also random effect models will be used (21). These models which represent a general approach to the problem of modeling repeated measurements with fairly general error structures, can allow for missing observations, serial correlations, time-varying covariates, and irregular measurement occasions. Second, for the description of the data, the association of covariates with the risk of an elevated antibody at a given point of time will be assessed using logistic regression models (22). A rather similar statistical approach was used in the DCCT Study (23).

The analyses of the second hypothesis will use the time of diagnosis of manifest type 1 diabetes as the only outcome measure. The dataset will thus be similar to that of a cohort study, and the statistical analyses will be carried out using the proportional hazards regression model (24) including the milk exposure as the risk factor and potential confounding factors a covariates in the model. Also time-dependent covariates can be included to assess the effects of potential modifying factors. The adjusted relative risk of type 1 diabetes between the two groups of milk exposure will be estimated. Also the adjusted incidence of the disease in the two groups can be assessed.

M. INTERIM ANALYSIS

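### Section L tests hypothesis 1 on visit-by-visit antibody status with no rule for visits after diabetes diagnosis, and it does not match the phase-1 outcome in Section H

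*Combined protocol and SAP*

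**What the plan says.** Section H (Follow-up Period during and after Intervention) lists visits ending at ages "9 and 10 years of age, or when clinical diabetes develops", and draws serology at those visits. The same section deals separately with the one-off DNA sample: "In the case of children who already have developed type 1 diabetes or have dropped-out from the follow-up", it is to be obtained separately where possible.

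Section L builds hypothesis 1 on repeated measurements: "At every time point the single antibody variable will be dichotomized as negative or positive". A child is positive at a visit when two or more antibodies are positive; diabetes is not part of that variable. The main tools are generalized linear and random-effect models, which "can allow for missing observations, serial correlations, time-varying covariates, and irregular measurement occasions". Logistic regression at a given time is added for description. No sentence says what value a child takes at visits after diagnosis.

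Two other places treat the same question differently. Section H (Outcome Assessment) defines the phase-1 outcome as autoantibodies, clinical diabetes or both by age 6. Section B plans Kaplan–Meier curves and a logrank test for time to autoimmunity or diabetes. Neither is named as primary for hypothesis 1, and neither are the Section L models.

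**The concern.** If serology stops at diagnosis, a child who becomes antibody positive and then diabetic counts as positive for some visits and is then absent. The absence is caused by the disease process under study. The Section L contrast becomes antibody prevalence among children still free of diabetes, a group formed after randomisation by an outcome the formula is meant to change.

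Two things are at stake. If the formula slows progression without preventing antibodies, more positive children stay under observation in the formula arm and it can look worse. If the formula does prevent antibodies, the comparison rests on fewer positives and loses power. In both cases the result does not estimate the phase-1 outcome that Section H defines.

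**Working it through.** **The plan's own figure.** For 7.6% diabetes by age 10 and "a reduction of 40% in the hazard rate of type 1 diabetes in the intervention group", Table 1 gives 1735, 1952 and 2032. I used exponential hazards, two-sided 5%, 80% power, 1:1 allocation (no ratio is stated), 4 years' uniform accrual and 10 years' further follow-up. This gives 1722 for the first and, with 20% exponential loss by 10 years, 1960 for the second. For the third, 1952/(1 − 0.10 × 0.40) = 2034. The plan's figures reproduce. After 20% drop-out, 2032 × 0.8 / 2 ≈ 813 per arm.

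**Model.** Negative → two or more antibodies (rate λ) → diabetes (rate μ), with constant hazards, every diabetic child first antibody positive, no reversion and no other drop-out. At age T:

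- negative: a = exp(−λT)
- positive, not diabetic: b = λ/(μ − λ) × [exp(−λT) − exp(−μT)]
- diabetic: d = 1 − a − b

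λ is −ln(1 − antibody frequency)/6. μ is solved so that d at age 10 equals the paired Table 1 diabetes frequency.

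| Table 1 pair (antibodies by 6 / diabetes by 10) | λ | μ | Control at age 6: a / b / d | Ever-positive already diabetic, d/(b + d) |
|---|---|---|---|---|
| 20.7% / 18.3% | 0.0387 | 0.186 | 79.3 / 12.2 / 8.5% | 41% |
| 18.5% / 15.4% | 0.0341 | 0.166 | 81.5 / 11.5 / 7.0% | 38% |
| 9.9% / 7.6% | 0.0174 | 0.142 | 90.1 / 6.6 / 3.3% | 33% |

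**Scenario A: progression ×0.6, seroconversion unchanged.** The true cumulative antibody ratio is 1.00. Prevalence among children still attending at age 6 is b/(a + b). Because a is the same in both arms, the odds ratio is the ratio of the two b values.

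- 20.7% row: 15.8% formula vs 13.4% control; 14.91/12.22 = 1.22
- 18.5% row: 14.5% vs 12.4%; 13.80/11.53 = 1.20
- 9.9% row: 7.9% vs 6.8%; 7.72/6.62 = 1.17

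Those are single-visit figures. A simulation of GEE over all visits to age 6 (20.7% row, 813 per arm) gave an odds ratio of 1.12 with independence working correlation (150 runs) and 1.07 with exchangeable (40 runs). With diagnosed children kept as positive, the independence estimate returned to 1.00.

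**Scenario B: seroconversion ×0.6, progression unchanged.** Power = Φ(|p₁ − p₂|/SE − 1.96), with SE² = p₁(1 − p₁)/n₁ + p₂(1 − p₂)/n₂.

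- 9.9% row, cumulative: 9.9% vs 6.06%, 813 per arm, SE 0.0134, power 82%. Among attenders: 6.84% vs 4.15%, n = 786 and 797, SE 0.0114, power 65%.
- 18.5% row: 98% cumulative, 88% among attenders.
- 20.7% row: 99% cumulative, 90% among attenders.

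The ratio among attenders is about 0.61 on every row, against true cumulative ratios of 0.61–0.63.

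**The case against.** The strongest reply is that the plan already contains analyses free of this problem. The Section H phase-1 outcome, the Section B logrank test and the cumulative frequencies in Table 1 do not lose a positive child at diagnosis. That stands, and it limits the point to Section L and to the missing statement of which analysis governs. It does not cure Section L, which sets out its own two methods for hypothesis 1 on an antibody-only variable.

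A reader might infer that the protocol plainly ends visits at diagnosis. It does not: the wording could also mean an extra visit at diagnosis. The sentence on the DNA sample supports the stopping reading but concerns one blood draw. If serology continues, no positives are lost. The remaining gap is that insulin autoantibodies (IAA) in insulin-treated children count without exception, and I have no calculation that makes this large.

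A reader might also infer that the trial is likely to report a false increase in antibodies. That needs slower progression with little effect on seroconversion. Hypothesis 1 is fewer antibodies, and under it the direction is preserved.

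Finally, the largest distortions belong to a single-visit contrast, which Section L calls descriptive. Over all visits they shrink, and a likelihood-based random-effect model, which also uses earlier positive samples, may be less affected (not simulated). But Section L fixes neither the working correlation nor the governing model, so this protection is not secured.

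**Conclusion.** The point holds as a gap in Section L and a mismatch between Sections B, H and L. It does not show that every planned antibody analysis is biased. On the likelier reading of Section H, 33–41% of ever-positive control children would be gone from the 6-year comparison. The cost is a spurious odds ratio of about 1.17–1.22 at that visit if the formula only slows progression (1.07–1.12 in GEE over all visits on the highest-risk row). If the formula works as hypothesised, the cost is a power loss from about 82% to 65% on the conservative row, and from 98–99% to 88–90% on the others.

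These sizes rest on constant hazards, antibodies always preceding diabetes, no reversion, and pairing the Table 1 rows. That diagnosed children were antibody positive is an assumption, not something the documents state. The sample size of 2032 is unaffected.

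**What to change.** In Section L, do one of the following:

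- count a child diagnosed with type 1 diabetes as having met the phase-1 outcome at every scheduled visit after diagnosis, instead of setting those visits to missing; or
- name the cumulative Section H composite, or the Section B time-to-event analysis, as primary for hypothesis 1.

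In either case, do not count IAA from samples taken after insulin has started. Leave observed antibody results in children without diabetes as measured; making positivity permanent for everyone would overwrite genuine later negatives that have nothing to do with diagnosis. Report the visit-level antibody-only model as a sensitivity analysis. Section H should also state which reading of its visit schedule is meant.

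The cost is a few sentences and one derived variable, with no new visits. The downside is that the rare child with diabetes but fewer than two antibodies counts as an event. A sensitivity analysis using the last sample at or before diagnosis shows whether that matters.
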